2.2.5 Eye Disorder Studies with CB-5339

Clinical evaluation of Cleave Therapeutics' first-in-class inhibitor of p97, CB-5083 in patients with advanced metastatic solid tumors (NCT02243917) and in lymphoid malignancies (NCT02223598) was halted due to dose-dependent toxicity related to PDE6 inhibition, including grade 2 chromatopsia, grade 2 photophobia, and grade 4 transient loss of vision that improved with drug discontinuation. Reporting rates for at least 1 eye disorder on the solid tumor and lymphoma studies were 25 of 32 subjects (78%) and 5 of 12 subjects (42%), respectively (data from 2016 IB). The median onset was day 1 for the solid tumor trial (range, 1 to 36), 60 to 90 minutes after dosing, and with a median duration of 60 to 120 minutes. Reports for the hematologic study were similar.

In dog toxicology studies with CB-5339 performed for the current proposed study, all animals had a normal ophthalmic and electroretinography (ERG) examinations throughout all phases, except for one male in the dose-ranging study administered 3.5 mg/kg/day, in which the left eye had a

white vitreous floater only at the pre-dose measurement. This was considered an incidental background finding. As noted in Section 2.2.4.2, no CB-5339-related ocular abnormalities were observed on slit-lamp biomicroscopy or indirect ophthalmoscopy during the dosing or recovery phases of the final repeat dose toxicity and toxicokinetic study 8376335.

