The pharmacokinetics of CB-5339 and an assessment of its effects on electroretinography (ERG) after a single oral dose to cynomolgus monkeys were measured (Study RPT-02-00032). In brief, three male cynomolgus primates were assigned to each dosing cohort: 10 mg/kg (low), 20 mg/kg (medium) and 40 mg/kg (high). Ophthalmic examinations and intraocular pressure (IOP) measurements were performed predose for all animals. ERG tests were performed predose and at approximately 3 and 24 hours postdose. At the predose ophthalmic examination, all the animals had a normal ophthalmic examination, and the baseline IOP values were within normal limits. CB-5339 was well tolerated, with no adverse clinical observations noted, following a single oral administration to male monkeys at the dose levels administered. The oral administration of CB-5339 at 40 mg/kg did not alter measures of retinal or retinal-cortical function in any of the animals when tested at 3 or 24 hours postdose. All ERG and visual-evoked potential (VEP) tests were within expected limits at baseline and there were no instances of significant depression of the ERG or VEP.

On this current clinical study, an ophthalmology examination including Optical Coherence Tomography (OCT), color vision testing, and a questionnaire will be performed by NEI associate investigators on all patients during screening. The questionnaire will be repeated after treatment on cycle 1 day 1 or 2, and if clinically indicated along with the ophthalmology exam (see [Appendix B](#)).

Characteristic	CB-5083	CB-5339
In vitro biochemical potency (nM)		
PDE6 IC ₅₀ (bovine)	27	380
PDE6 IC ₅₀ (human)	310	3900
In vivo rat tissue distribution		
rat C _{max} retina/plasma ratio	2.5	0.08
rat AUC retina/plasma ratio	4.3	1.1

Figure 9: CB-5339 is 10x less potent on PDE6, has 4x lower retinal penetration and does not cause electroretinographic effects at a similar AUC than CB-5083.

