Labs (CBC with differential; serum chemistries) will be performed at baseline (within 8 days of the start of protocol therapy), during weeks 1, 2, 3, and 4 of cycle 1, and at the start (+/- 1 day during the cycle and up to 3 days before start of a new cycle) and during week 1 of every cycle thereafter. For the first three patients enrolled on the study who will receive their initial week of treatment as inpatients, labs will also be performed on Cycle 1 Day 2 prior to CB-5339, on Day 3 based on the result from Day 2, on Day 4 prior to CB-5339, on Day 6 (Sunday at the Day Hospital), and on Day 8 (C1W2).

ECG will be performed at baseline (within 8 days of the start of protocol therapy) and will be

performed on day 1 pre-dose and at 2 hours post dose/the time to peak concentration of every subsequent cycle, and as clinically indicated.

Blood and urine samples for correlative PD and PK studies will be collected from all patients as described in [Section 7](#).

Paired tumor biopsies will be collected at baseline and then 4-6 hours after receiving the first dose in the expansion cohort; an optional biopsy may be collected at disease progression or “pre-progression” (defined as a 10-19% increase in tumor volume as shown on a restaging scan).

NEI associate investigators will perform an ophthalmology examination that includes optical coherence tomography (OCT), color vision testing, and a questionnaire on all patients during screening. The questionnaire will be repeated after treatment on cycle 1 day 1 or 2; the questionnaire and eye examinations can be repeated by NEI as clinically indicated. Details about the questionnaire and eye examinations can be found in [Appendix B](#) along with thresholds for pre-existing visual impairment. Patients should be encouraged to report any vision changes to the study team immediately.

CB-5339 is administered orally on a schedule of once daily, 4 days on and 3 days off (28-day cycle). Dose escalation will continue until the RP2D (MTD) is established. Intra-patient dose escalation will be permitted; refer to Section 5.2 regarding conditions for permitted intra-patient dose escalation.

Dose Escalation Schedule	
Dose level	Dose of CB-5339 (mg/day, once daily 4 days on/3 days off weekly)
-1	25 mg/day; 3 days on/4 days off
1 (starting)	25
2	50
3	100
4	150
5	225
6	300

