- e. Blood and urine for PK analysis will be obtained from all patients as specified in [Section 7.1](#).
- f. Blood samples for PBMCs (mandatory for all patients except for an optional sample at/near disease progression) will be collected from patients as specified in [Section 7.2](#).
- g. Blood samples for ctDNA (mandatory only during expansion phase) will be collected from patients as specified in [Section 7.2](#).
- h. An ophthalmology examination and questionnaire will be conducted on all patients during screening by NEI investigators; the questionnaire will be repeated by the patient after treatment on cycle 1 day 1 or 2, and as clinically indicated with the eye exam per [Appendix B](#).
- i. Values from eligibility screening tests may be used as baseline evaluation values if the test was performed within 8 days of start of protocol therapy (or, for radiologic evaluation, ECHO, and tumor measurement, within 28 days of start of protocol therapy). See [Section 3.4](#).

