APPENDIX B: PATIENT OPHTHALMOLOGIC QUESTIONNAIRE AND EYE EXAM

Today's date _____

Agent: CB-5339

[figure not shown]
Patient Name _____ (*initials acceptable*) Patient Study ID _____

Reason for questionnaire (screening/Cycle 1 day 1 or 2/as clinically indicated): _____

[figure not shown]
Please complete this form by placing an "X" on the line marking a place on the scale that indicates your answer to the questions about your eyes and vision.

For us to best understand the status of your eyes and vision and how they affect your quality of life, your answers must be as accurate as possible. If you wear glasses or contact lenses to improve your vision, please answer all of the following questions as though you were wearing them.

1. How would you describe your vision in your right eye, on average, over the past month?

[figure not shown]
2. How would you describe your vision in your left eye, on average, over the past month?

Blind / No vision whatsoever

Perfectly normal vision

[figure not shown]
4. How would you describe your vision in your right eye today?

Blind / No vision whatsoever

Perfectly normal vision

[figure not shown]
5. How would you describe your vision in your left eye today?

Blind / No vision whatsoever

Perfectly normal vision

[figure not shown]
6. How would you describe the way your eyes have felt on average over the past month?

At least one eye has been very painful

No discomfort in either eye

[figure not shown]
7. How would you describe the way your eyes feel today?

At least one eye is very painful

No discomfort in either eye

[figure not shown]
8. Have you noticed any visual disturbances in either eye over the past month?

Severe visual disturbances

[figure not shown]
No visual disturbances

9. Do you notice any visual disturbances in either eye today?

[figure not shown]

C1D1 or D2

[figure not shown]
10. How would you describe your vision in your right eye, on average, since you started taking study drug?

[figure not shown]
11. How would you describe your vision in your left eye, on average, since you started taking study drug?

[figure not shown]
12. How would you describe your vision in your right eye today?

13. How would you describe your vision in your left eye today?

[figure not shown]
14. How would you describe the way your eyes have felt on average since you started taking study drug?

[figure not shown]
At least one eye has been very painful

No discomfort in either eye

[figure not shown]

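### Only one post-dose eye questionnaire is scheduled (cycle 1 day 1 or 2, no clock time), so no fixed eye-specific question covers the rest of the cycle that drives escalation

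*Combined protocol and SAP*

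**What the plan says.** Four places give the same schedule.

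- Section 5: "The questionnaire will be repeated after treatment on cycle 1 day 1 or 2". After that, "the questionnaire and eye examinations can be repeated by NEI as clinically indicated".
- Section 2.2.5: "The questionnaire will be repeated after treatment on cycle 1 day 1 or 2, and if clinically indicated along with the ophthalmology exam".
- Section 10, ophthalmic footnote: "the questionnaire will be repeated by the patient after treatment on cycle 1 day 1 or 2, and as clinically indicated with the eye exam". The calendar row is marked only at screening and in cycle 1 week 1.
- Appendix B, the form itself: "Reason for questionnaire (screening/Cycle 1 day 1 or 2/as clinically indicated".

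None of them says how long after the dose the form is to be completed.

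For CB-5083, Section 2.2.5 reports at least one eye disorder in 25 of 32 solid tumor patients and 5 of 12 patients in the lymphoid trial. It adds: "The median onset was day 1 for the solid tumor trial (range, 1 to 36), 60 to 90 minutes after dosing". Median duration was 60 to 120 minutes, and reports from the second trial were similar. The CAEPR in Section 9.1.1 lists six eye terms as possibly related to CB-5339, all carried over from CB-5083.

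Under Section 5.2, the accelerated phase treats one patient per dose level and ends at the first drug-related Grade 2 toxicity in cycle 1.

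**The concern.** The schedule fits the typical onset but not the reported spread. Events that last an hour or two and resolve unaided are easily left unmentioned at a visit days later unless someone asks.

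The consequence falls on escalation. Section 2.2.5 describes Grade 2 chromatopsia and Grade 2 photophobia on CB-5083. One such event in cycle 1, if drug-related, would switch this trial to 3+3. With one patient per level, a single unrecorded event is enough to let single-patient escalation continue. The protocol gives ocular toxicity its own treatment: it is the exception in Section 5.9.1 and the subject of Section 5.10. Those provisions work only on symptoms that come to light.

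**Working it through.** **1. The plan's own figures.** 25/32 = 78.1% and 5/12 = 41.7%, matching the stated 78% and 42%.

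**2. Doses with no scheduled form after them.** Four doses a week for four weeks gives 4 × 4 = 16 doses in cycle 1. The form follows dose 1 or, at the latest, dose 2. That leaves 16 − 2 = 14 to 16 − 1 = 15 doses, or 14/16 = 88% to 15/16 = 94%.

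**3. Timing on days 1 and 2.** Adding the reported onset and duration gives typical resolution between 60 + 60 = 120 and 90 + 120 = 210 minutes (2 to 3.5 hours) after a dose. The durations are medians, so this is a guide and not a limit.
- A day 1 form completed in the first hour precedes the reported onset.
- On a day 2 form completed before the second dose, items such as "How would you describe your vision in your right eye today" describe a time about 24 − 3.5 = 20.5 hours or more after typical resolution.
- Items 10, 11, 14 and 16 look back to the start of study drug, so a day 2 form can still pick up a day 1 event. Items 10, 11 and 14 ask for an average; item 16 asks about any disturbance.
- The PBMC draw at 4 to 6 hours falls 0.5 to 2.5 hours after the 3.5-hour point.

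**4. How many onsets were late.** Assume the median and range describe first onset in the 25 affected solid tumor patients. A median of day 1 then means at least 13 of 25 began on day 1. Between 1 and 12 (4% to 48%) began later, at least one of them on day 36. The documents do not narrow this.

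**5. Where day 36 falls.** 36 − 28 = 8, so it is cycle 2 day 8. This is a dosing day, 8 days after cycle 1 ends.

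**6. What repeat forms would reach.** The last nominal cycle 1 dose is on day 25. Cycle 2 starts on day 29, and its examination may be up to 3 days earlier, on day 26. A look-back form at that visit therefore covers all 16 cycle 1 doses. Cycle 3 starts on day 57, or day 54 if examined 3 days early, so a form there looks back over day 36.

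**The case against.** The strongest case against is that other monitoring is already substantial.

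- Section 5 requires history and physical examination in each week of cycle 1 and at every later cycle start, and the calendar has an adverse event evaluation row.
- The diary has a comments space for each dose, asks for side effects, and tells patients to call about vision changes. Symptoms lead to an unscheduled eye examination under Section 5.10.
- Mandatory PK draws at 1, 2, 4, 6 and 24 hours keep patients in contact with staff through the usual symptom window of the first dose.
- The first three patients are inpatients for five days, covering doses 1 to 4. If escalation is uninterrupted, these are the patients at 25, 50 and 100 mg.

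All of this stands. A reader might infer that later detection depends wholly on spontaneous reports, or that 88% to 94% of doses are unmonitored. The documents do not support either reading: the percentage counts one form only. What remains is narrower. None of these routes is a scheduled eye-specific question. The inpatient stay leaves 16 − 4 = 12 cycle 1 doses outside it for those three patients, and patients from the fourth onward have no such stay.

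The second objection is that the onset data belong to another drug. That also stands. The protocol attributes the toxicity to off-target PDE6 inhibition and reports CB-5339 as about 10-fold less potent there, without electroretinographic effects. It would be wrong to call this an established class effect or a known effect of CB-5339. But the CAEPR still lists the events as possible, and the trial is described as first-in-human.

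**Conclusion.** The point holds as a cheap improvement to safety ascertainment. It is not an error or an internal contradiction: the four statements of the schedule agree, and the form targets the median onset day. The gap is that no fixed eye-specific question is asked on days 3 to 28, while one transient drug-related Grade 2 event there would change the escalation scheme. A second, smaller gap is the missing clock time for the one form that is scheduled.

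A reader might infer from day 36 that dose-limiting toxicity decisions would be wrong. They would not be affected by an event on that day, because Section 5.2 confines them to cycle 1. Day 36 bears only on the wider safety and tolerability objective.

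The conclusion assumes that CB-5083 timing is a reasonable guide for CB-5339, and that brief mild symptoms are sometimes not volunteered. The documents give no figure for how often that happens, so the number of events missed cannot be estimated.

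**What to change.** In Section 5, the Section 10 ophthalmic footnote and calendar row, and Appendix B (reason line and item block):

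- **(a)** State that the first post-dose form is completed after the reported symptom window, for example with the 4 to 6 hour PBMC draw on day 1 or at the 24-hour PK draw on day 2.
- **(b)** Repeat the existing items that look back to the start of study drug at the already scheduled cycle 1 week 2, 3 and 4 visits and at the start of cycles 2 and 3.

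Because those items look back, the later forms need not fall on a dosing day or at a set interval after a dose, and no home form is needed for day 36. Patients who stop before cycle 3 will not reach the last form.

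The cost is about five more short forms per patient (3 + 2) at existing visits, and some additional minor visual complaints to review under Section 5.10 as it stands. No change to dosing or management rules is proposed.

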5.1 Agent administration

CB-5339 will be administered once daily, 4 days on and 3 days off, in 28-day cycles. CB-5339 capsules should be taken in a fasted state, either 1 hour before or 2 hours after meals. Patients have a 6-hr window to make up for missed/vomited doses.

Reported adverse events and potential risks are described in [Section 9](#). Appropriate dose modifications are described in [Section 5.9](#). No investigational or commercial agents or therapies other than those described below may be administered with the intent to treat the patient’s malignancy.

After cycle 2, as a measure of patient compliance only, a cycle will be considered completed if 90% of the prescribed CB-5339 doses are administered.

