2.3 Rationale

Based on its well characterized mechanism of action, preclinical data, and experience with Cleave's previous-generation p97 inhibitor, CB-5339 may provide benefits to patients with advanced solid tumors and lymphomas refractory to standard-of-care treatments. The anticancer effects of CB-5339 have been characterized in several *in vitro* and *in vivo* pharmacology studies and an ongoing trial in canine patients, demonstrating that it can elicit a variety of biological effects including induction of an unfolded protein response, decreased cell viability, and apoptosis. The study-objective recommended phase 2 dose (RP2D) will be determined by the following: (1) a dose no higher than the maximum tolerated dose level; (2) obtaining exposures associated with preclinical biomarker activity; and (3) patient responses.

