5. TREATMENT PLAN

This is a first-in-human, open-label phase 1 trial of oral CB-5339 in adult patients with advanced metastatic solid tumors and lymphoid malignancies. The study will be conducted in two parts, an initial dose-escalation phase followed by a dose expansion phase at the recommended phase 2 dose (RP2D) in the same patient population. Additional expansion cohorts may be considered to explore pharmacodynamic endpoints at lower dose levels (a protocol amendment will be submitted for these changes to the trial design).

Patients will be required to maintain a study diary documenting when the doses were taken, and any associated side effects ([Appendix D](#)). Patients will be asked to return the diary to the clinic staff at the end of each cycle.

Patient evaluations will be performed throughout the study as described below. Baseline history, physical examination, laboratory evaluations, and ECG must be conducted within 8 days prior to start of protocol therapy. If protocol therapy is started within 8 days of the eligibility screening evaluations (see [Section 3.4](#)), the results from these screening evaluations may be used as baseline measurements. If > 8 days have passed since the screening evaluations, the medical history, physical examination, laboratory evaluations, and ECG must be repeated prior to starting protocol therapy.

Baseline tumor imaging must be performed within 28 days prior to start of protocol therapy. If protocol therapy is started within 28 days of the eligibility screening tumor imaging, the screening evaluation imaging results may be used as baseline measurements; if > 28 days have passed since the screening evaluation tumor imaging, the imaging must be repeated prior to starting protocol therapy.

History and physical examination will be performed at baseline (within 8 days of the start of protocol therapy), during weeks 1, 2, 3, and 4 of cycle 1, and at the start of every cycle thereafter (within 3 days prior to treatment). Physical examinations will include O₂ saturation measured by pulse oximeter.

The first three patients on study will be admitted to the NIH Clinical Center for 5 days of in-patient evaluation followed by out-patient evaluation at the day hospital on days 6 and 7 (vital check, PO₂, serum chemistries, and CBC).

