5.2 Definition of Dose-Limiting Toxicity

Determination of dose-limiting toxicity (DLT) will be based on toxicities observed in the first cycle of therapy and felt to be at least possibly related to study drug. A greater than 2-week delay for AEs before cycle 2 would be considered a DLT.

This study will follow design 3 of the Simon accelerated titration designs (Simon et al., 1997). We will accrue to the next dose level only after we have established safety at lower dose levels.

During this accelerated phase, there will be one patient per dose level. After the first instance of a drug-related Grade 2 toxicity (during the first cycle) at any dose level, the accelerated phase will end, and dose escalation will be changed to a 3 + 3 design. All decisions on dose expansion and DLT will be made on the first cycle of treatment.

When the accelerated phase ends, the trial will go back to a traditional 3+3 design. That is, additional patients will be placed on the dose level at which the last new patient was treated; 3 patients will be treated initially at each new dose level.

Number of Patients with DLT at a Given Dose Level	3+3 Escalation Decision Rule
0 out of 3	Enter 3 patients at the next dose level.
≥ 2	Dose escalation will be stopped. This dose level will be declared the maximally administered dose (highest dose administered). Three (3) additional patients will be entered at the next lowest dose level if only 3 patients were treated previously at that dose.
1 out of 3	Enter at least 3 more patients at this dose level. 
• If 0 of these 3 patients experience DLT, proceed to the next dose level.• If 1 or more of this group suffer DLT, then dose escalation is stopped, and this dose is declared the maximally administered dose. Three (3) additional patients will be entered at the next lowest dose level if only 3 patients were treated previously at that dose.
≤ 1 out of 6 at highest dose level below the maximally administered dose	This is generally the recommended phase 2 dose. At least 6 patients must be entered at the recommended phase 2 dose.

If ≥ 2 patients experience DLT on dose level -1, the study will be placed on hold and all data reviewed to make a decision about further evaluation of the study drug.

DLT is defined as an adverse event that is related (possibly, probably, or definitely) to

administration of study drug and fulfills one of the following criteria:

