APPENDIX C: PD/PK COLLECTION WORKSHEETS

7.1 Pharmacokinetic Analysis

CB-5339 pharmacokinetics will be measured in plasma and urine from all patients during cycle 1 day 1 (the first 3 patients will also have PK blood collected on C1 D4) and during subsequent cycles for patients experiencing toxicity or who have undergone intra-patient dose escalation. A stability additive must be included in urine samples as described below. PK parameters, including area under the plasma concentration versus time curve (AUC), maximum plasma concentration (C_{max}), trough plasma concentration (C_{min}), time to maximum plasma concentration (T_{max}) and plasma terminal elimination half-life ($T_{1/2}$) will be determined using appropriate PK models. PK samples will be batched for analysis at the conclusion of the escalation phase and will not be used to determine escalation or expansion phase doses. *Note: the 8-hr post dose sample collection is optional pending data on agent stability in whole blood overnight until processing.*

One 0.5 mL K₂EDTA tube (pediatric microtainer) will be obtained for each of the time points. The actual time of collection will be noted for each sample, and the sample will be placed immediately on wet ice until processing to plasma.

Blood will be collected at the following times (mandatory all patients except for the 8-hr post dose collection):

- cycle 1 day 1 prior to CB-5339 administration
- cycle 1 day 1 at 15, 30, and 60 minutes, 2hr, 4hr, 6hr, 8hr*, 24hr after CB-5339 (before another dose is taken)

Blood will also be collected at the following times for the first 3 patients only who will be admitted to the Clinical Center until Day 5 (all mandatory except for the 8-hr post dose collection):

- cycle 1 day 4 predose and at 15, 30, and 60 minutes, 2hr, 4hr, 6hr, 8hr*, 24hr after CB-5339 (before another dose is taken)

Patients who have been dose-adjusted will have optional PK samples collected prior to CB-5339 administration on day 1 and then 1, 2, and 24 hours after drug administration (before another dose is taken) during the first cycle following dose adjustment only.

The PK blood tubes/samples should be kept on ice until plasma can be recovered, at which time the plasma samples should be frozen (-70°C). The plasma samples should be stored at -70°C, and shipped to the PK lab at the address below on dry ice.

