- Samples from the first three patients (hospitalized) will be sent in individual batches (i.e., all plasma from the patient's day 1 and 4 collections) for "real-time" PK analysis by validated HPLC-MS/MS. Subsequent patient samples can be stored and batched for shipment (approximately 48 samples/shipment).

A baseline urine collection of 10 mL will be collected just before CB-5339 administration. **1.5% BSA will be added to the sample and mixed well.** Urine will then be collected at

every void from 0 to 24 hours on cycle 1, day 1 for PK analysis. Samples should be placed on wet ice immediately after collection and then refrigerated in the presence of 1.5% BSA. The total volume of urine collected for the 24-hour time period will be documented and a 10-mL sample will be taken from the total volume and saved; the rest can be discarded. PK samples will be shipped to:

Attn: [name]
Alturas Analytics
[name]
[name]
[contact]

Based upon the results of the initial measurements, sampling times may be adjusted but neither the total number of samples nor the total amount of blood will be increased.

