APPENDIX D: PATIENT STUDY DIARY

Today's date _____

Agent: CB-5339 Dose: _____

Patient Name _____ (*initials acceptable*)

Patient Study ID _____

INSTRUCTIONS TO THE PATIENT:

1. Complete one form for each cycle (28 days, or 4 weeks) of treatment.
2. You will take _____ capsules (____ mg per capsule) of CB-5339 once daily on days 1-4 each week for each cycle. Take your dose at approximately the same time each day. CB-5339 should be taken with water only on an empty stomach (that is, at least 1 hour before or 2 hours after a meal).
3. Record the date and times when you took CB-5339.
4. If you miss or vomit the dose within 6 hours, please make a note of this in the Comments column and do not make up the dose.
5. If you have any comments or notice any side effects, please record them in the Comments column. **If you have any changes in vision, please call the study team immediately.**
6. Please bring this form and any unused CB-5339 when you return for each appointment.

[figure not shown]
Day	Date	Time of CB-5339 dose	Dose Taken	Comments
1	Week 1			
2				
3				
4				
5	Do not take CB-5339 today			
6	Do not take CB-5339 today			
7	Do not take CB-5339 today			
8	Week 2			
9				
10				
11				
12	Do not take CB-5339 today			
13	Do not take CB-5339 today			
14	Do not take CB-5339 today			

15	Week 3			
16				
17				
18				
19	Do not take CB-5339 today			
20	Do not take CB-5339 today			
21	Do not take CB-5339 today			
22	Week 4			
23				
24				
25				
26	Do not take CB-5339 today			
27	Do not take CB-5339 today			
28	Do not take CB-5339 today			

Patient's signature: _____

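### For a dose vomited within 6 hours, Section 5.1 permits a make-up dose and patient diary item 4 (Appendix D) tells the patient not to take one; nothing in the available text says which rule applies

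*Combined protocol and SAP*

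**What the plan says.** Section 5.1 (Agent administration) sets the rule for the protocol body: "Patients have a 6-hr window to make up for missed/vomited doses". It does not say when the 6 hours start.

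Appendix D (Patient Study Diary), instruction 4, addresses the patient directly. Its condition is "If you miss or vomit the dose within 6 hours" and its instruction is "please make a note of this in the Comments column and do not make up the dose".

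The diary is not optional. Section 5 states: "Patients will be required to maintain a study diary documenting when the doses were taken".

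Three other places come close to the subject without settling it:

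- Section 5.8 (Dosing delays) says that interrupted dosing is not made up, whatever the reason. It sits among the rules on holds and delays and mentions neither vomiting, Section 5.1 nor the diary.
- Section 5.4.1 (Nausea/Vomiting) deals with anti-emetics only.
- The study calendar footnotes in Section 10 give the dosing pattern and fasting rule and say nothing on re-dosing.

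**The concern.** Staff work from Section 5.1 and patients work from the diary. For the same event, a dose brought up shortly after intake, one text allows another capsule and the other rules it out. Two patients at one dose level could then receive different amounts of drug although both followed a current study document.

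The timing makes this worth correcting. This is a first-in-human trial, and Section 5.2 states: "All decisions on dose expansion and DLT will be made on the first cycle of treatment". Vomiting is a foreseeable event: it is on the Section 9.1.1 risk list, anti-emetics are not given routinely before dosing (Section 5.4.1), and vomiting leads to dose modification only when refractory to treatment (Section 5.9.2). Patients may therefore keep dosing through vomiting, which is when the rule is needed. Exposure also has a stated role, since the second of the three RP2D considerations in Section 2.3 is "2) obtaining exposures associated with preclinical biomarker activity".

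**Working it through.** The plan gives no figure to reproduce. The check has two parts: a comparison of the texts, then a bound on how far the two rules can move the dose.

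**Comparison of the texts**

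| Event | Section 5.1 | Diary item 4 | Result |
|---|---|---|---|
| Dose vomited 1 hour after intake | Make-up allowed, whether the window runs from intake or from vomiting | No make-up | Opposed |
| Dose missed, remembered 3 hours late | Make-up allowed | Depends on the reading | Ambiguous |
| Dose missed, remembered 8 hours late | Outside a window counted from the usual dosing time | No make-up under the skip-if-late reading | Compatible |

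For a missed dose, the diary's condition can mean that a dose not taken within 6 hours is skipped, which agrees with Section 5.1. It can also mean that a dose missed by less than 6 hours is not made up, which does not agree. For a vomited dose, the natural meaning is vomiting within 6 hours of intake, and there the instruction opposes the permission in Section 5.1.

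**Bound on the dose difference**

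Inputs: four dosing days a week for four weeks at levels 1 to 6; three dosing days a week for four weeks at level -1 (dose escalation schedule, Section 5). Planned doses in cycle 1:

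- Levels 1 to 6: N = 4 × 4 = 16
- Level -1: N = 3 × 4 = 12

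Let f be the fraction of the vomited dose that was absorbed and r the fraction of the repeat dose that is retained. Both lie between 0 and 1, and the documents give neither. For one vomited dose in the cycle:

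- Not retaken: N − 1 + f doses
- Retaken: N − 1 + f + r doses
- Difference: r doses, between 0 and 1 whatever f is

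As a share of the planned cycle-1 amount, the difference is r/N:

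- Levels 1 to 6: at most 1/16 = 6.25%
- Level -1: at most 1/12 = 8.3%

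Example at 225 mg (level 5). Plan: 16 × 225 = 3,600 mg.

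- Not retaken: 15 × 225 = 3,375 mg (f = 0) to 3,600 mg (f = 1)
- Retaken and fully kept (r = 1): 3,600 mg (f = 0) to 17 × 225 = 3,825 mg (f = 1)
- Retaken and wholly lost (r = 0): the same range as not retaken

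The largest difference for a given f is one dose, 225 mg.

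For scale, the escalation steps 25, 50, 100, 150, 225, 300 mg are increases of 100%, 100%, 50%, 50% and 33.3%. The smallest, 225 to 300 mg, is 75/225 = 33.3%, so one vomited dose moves the cycle total by much less than any step.

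**Frequency**

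Section 9.1.1 lists vomiting, but its footnote says that every listed event comes from the related compound CB-5083, and the list carries no frequencies. No per-patient or per-cohort figure can be given.

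**The case against.** The strongest reply is that Section 5.1 is permissive. It requires nobody to re-dose, so a patient who follows the diary complies with both texts. Every patient holds the same diary, so practice may be uniform unless staff advise otherwise. This is correct as far as it goes. It does not remove the conflict: staff who follow Section 5.1 may allow a repeat dose that the diary refuses.

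A second reply is that diary item 4 is clumsy, and that if its condition can be read loosely for missed doses it can be read the same way for vomited ones. That stands for missed doses. For vomited doses it requires supplying words that are not there, and if it was the intent, the diary still needs correcting.

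A third is that Section 5.8 already settles the matter. Read broadly it leans towards the diary, but it would then itself contradict Section 5.1, and it is not written as a rule of precedence. The public copy also lacks some pages, including Appendix F, so the statement that nothing settles the rule is limited to the available text.

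Three stronger inferences are tempting, and the documents do not support them.

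- *DLT misclassification.* Section 5.2.1 counts doses against a 75% threshold, which is 12 of 16. Falling below it needs five vomited, unreplaced doses (11/16 = 68.75%) and the assumption that a vomited dose is not counted as administered, which the protocol does not state. The 90% figure in Section 5.1 applies only after cycle 2 and only as a compliance measure.
- *Doubling of the assigned dose.* A same-day amount of up to 2.0 times the assigned dose needs full absorption before vomiting and full retention of the repeat. It is a property of re-dosing itself and would remain if both texts allowed it, so it does not measure the conflict.
- *Distorted escalation through PK.* For the first three patients, "Samples from the first three patients (hospitalized) will be sent in individual batches" for real-time analysis, but their day-1 and day-4 sampling falls within the inpatient stay, under direct observation. Section 7.1 also says that PK results "will not be used to determine escalation or expansion phase doses".

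**Conclusion.** The point holds: for a dose vomited within 6 hours, the protocol body and the patient diary give opposing instructions, and the available text does not resolve them. This is wrong as written rather than a missing detail. For missed doses the fault is only ambiguity.

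The size is modest. The difference is at most one dose per vomited dose: up to 6.25% of the planned cycle-1 amount at levels 1 to 6 and up to 8.3% at level -1. Both maxima assume a fully retained repeat dose; if the repeat is also lost the difference is zero. How often the situation will arise is unknown. No misclassified DLT, effect on escalation or effect on the RP2D is shown. The case for acting rests on consistent dosing and clear patient instructions in the cycle that decides DLTs, and on how little the correction costs.

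**What to change.** Put one identical rule in Section 5.1 and in diary item 4, treating missed and vomited doses separately, and reissue the diary. Suggested default:

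- A missed dose may be taken up to 6 hours after the usual time and is otherwise skipped.
- A vomited dose is recorded and not retaken. This is the diary's existing rule and the more cautious one in a first-in-human trial.

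If the sponsor confirms that re-dosing after vomiting is intended, keep Section 5.1 for vomited doses, correct the diary to match, and have the repeat-dose time written in the existing time and comments fields of the diary and the day-1 collection sheet, so that affected day-1 PK and PD profiles can be identified.

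In either case, add a phrase to Section 5.8 making clear that its no-make-up sentence covers held or interrupted dosing.

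The cost is a short protocol edit and a reissued diary. No visits, samples or patients are added.
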